8.6.4 Sensitivity Analysis

The sensitivity analysis is to evaluate the assumptions of using the mGCSI-DD in the primary analysis of patients discharged from the hospital without solid food tolerance. Time to solid food tolerance for patients who could not tolerate solid food during the hospital will be censored to 168 hours if the patient is discharged from the hospital during the study and not tolerating solid food. If the subject was not discharged from the hospital during the study and did not tolerate solid food, the time to solid food tolerance will be censored at the latest date and time of the hospital stay.

8.6.5 Supplementary Analyses

Time to solid food tolerance through the Day 30 visit will be displayed using a Kaplan-Meier estimate and will be compared between the 3 treatment groups and the placebo group using a stratified log-rank test stratified by eCRF recorded sex (male or female) and the risk for organ failure (higher or lower) based on eCRF data.

Supplementary analysis 1: The definition of time to solid food tolerance and the censoring method follow the primary analysis method.

Supplementary analysis 2: The definition of time to solid food tolerance and the censoring method follow the sensitivity analysis method.

8.7 Secondary Endpoint Analyses

8.7.1 Percentage of Patients who Tolerated Solid Food at 48, 72, and 96 Hours from the SFISD and at Discharge

Solid food tolerance will be calculated using the main analytical approach as described in Section 8.6.3.

If the time to first solid food tolerance \leq 48 hours then solid food tolerance at 48, 72 and 96 hours are all yes.

If the time to first solid food tolerance >48 and \leq 72 hours, then solid food tolerance at 72 and 96 hours are all yes and solid food tolerance at 48 hours is no.

If the time to first solid food tolerance >72 and <96 hours, then solid food tolerance at 96 hours is yes and solid food tolerance at 48 and 72 hours are all no.

Protocol CM4620-203 CONFIDENTIAL Page 18 of 31

If the time to first solid food tolerance > 96 hours or the patient never tolerates the solid food during the study then solid food tolerance at 48, 72, and 96 hours are all no.

If the time to first solid food tolerance ≤time to hospital discharge, solid food tolerance at discharge is yes, otherwise, solid food tolerance at discharge is no. If a patient was not discharged from the hospital before end of study, solid food tolerance at the end of study is no.

If it is unknown if solid food has been tolerated at a specific time point (time to first solid food tolerance is censored before the specific time point), the solid food tolerance will be imputed as no.

The proportion and 95% CI of patients who tolerated solid food at 48, 72, and 96 hours from the SFISD, at discharge, and at the end of the study will be displayed using a Clopper-Pearson interval and will be compared between each Auxora treatment group and placebo group using a Cochran-Mantel-Haenszel test stratified by the eCRF recorded sex (male or female) and the risk for organ failure (higher or lower) based on eCRF data. Prohibited immunosuppressive medications or immunotherapies and treatment discontinuation will be ignored (treatment policy strategy).

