5.3 Discharge Criteria

The patient randomized to receive study drug should remain in the hospital until all 3 doses of study drug have been administered. The criteria for medically indicated discharge from the hospital are:

- Abdominal pain has resolved or is controlled with medications;
- Solid food is tolerated, which is defined as eating ≥50% of a low fat, ≥500 calorie solid meal without an increase in abdominal pain or vomiting;

• There is no clinical evidence of an infection necessitating continued hospitalization.

In the scenario where the PI or treating physician wants the infusion(s) to begin earlier than the 24 hour +/- 1 hour window (e.g. the patient is ready to be discharged before all 3 doses of study drug have been administered and / or to facilitate an infusion time where study personnel are available), the PI or treating physician should contact the medical monitor to discuss whether it is appropriate to begin infusion earlier (up to 6 hours earlier) than the 24 hour +/- 1 hour protocol window.

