8.6.3 Main Analytical Approach

Time to solid food tolerance through Day 30 visit will be analyzed based on the Generalized Multiple Comparison Modelling (gMCP-Mod) approach described in Session 8.6.1.

Time to solid food tolerance is defined as the number of hours from the date and time of the SFISD for the patient to the first date and time the patient receives a solid meal that is tolerated. If the mealtime was not recorded, the mealtime will be estimated using the middle time of the meal serving interval.

Tolerating a solid meal is defined as eating \geq 50% of a low fat, \geq 500-calorie solid meal without an increase in abdominal pain or vomiting within the two hours of mealtime. In addition, to meet the definition, all subsequent meals during the hospitalization should not show an increase in abdominal pain or vomiting within the two hours of mealtime. If a procedure that could impact food tolerance is performed after a solid meal is initially tolerated that results in subsequent meals not being tolerated, the time of the initial tolerated meal will be considered in the calculation of the time to solid food tolerance. The procedures that impact food tolerance and/or its assessment are defined as (1) a procedure that requires a period of nil by mouth (2) a procedure and/or treatment that causes gastrointestinal dysfunction e.g., cholecystectomy, necrosectomy. The procedures performed after the initial food tolerance will be reviewed before the database lock to identify the procedures that could impact the time to the tolerated solid food. If the subject was not discharged from the hospital during the study and did not tolerate solid food, the time to solid food tolerance will be censored at the latest date and time of the hospital stay.

If a patient is discharged home without tolerating solid food, the daily record of the modified American Neurogastroenterology and Motility Society Gastrointestinal Cardinal Symptom Index Daily Diary (mGCSI-DD) at or after hospital discharge will be used in the calculation of the time to solid food tolerance. The patients who did not tolerate solid food while hospitalized will be considered as tolerating solid food at or after hospital discharge at 8am on the first of three consecutive days where the following 4 criteria are met for the mGCSI-DD:

Protocol CM4620-203 CONFIDENTIAL Page 17 of 31

- none for vomiting
- none or mild for nausea

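### SAP 8.7.1 scores every patient still in hospital at the end of study as not tolerating solid food, even when Section 8.6.3 counts the same patient as tolerating it

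*SAP*

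**What the plan says.** SAP 8.7.1 ties the binary tolerance endpoints to the primary definition: "Solid food tolerance will be calculated using the main analytical approach as described in Section 8.6.3".

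Under SAP 8.6.3 the event time is "the first date and time the patient receives a solid meal that is tolerated". Tolerance must also be sustained: "all subsequent meals during the hospitalization should not show an increase in abdominal pain or vomiting within the two hours of mealtime". There is an exception for procedures that interfere with eating. Discharge is not part of the definition. The censoring rule for inpatients carries two conditions joined by *and*: "If the subject was not discharged from the hospital during the study and did not tolerate solid food". The sensitivity analysis in 8.6.4 repeats both conditions.

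After its rule for status at discharge, 8.7.1 states: "If a patient was not discharged from the hospital before end of study, solid food tolerance at the end of study is no". This sentence has only the discharge condition.

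The end of study is then analysed as a time point of its own. The proportions at 48, 72 and 96 h, "at discharge, and at the end of the study will be displayed using a Clopper-Pearson interval", and each Auxora group is compared with placebo by a CMH test stratified by sex and risk of organ failure.

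**The concern.** Two rules in the same plan classify the same patient in opposite ways. Section 8.7.1 adopts the 8.6.3 definition and then, for one time point, replaces it with a rule that looks only at discharge.

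The end-of-study proportion is presented as a measure of food tolerance. For patients who remain in hospital it measures whether they have gone home. A difference between arms at that time point could then reflect tolerance, long stays for other reasons, or both, and the CMH test cannot separate them. A reader would also see a patient counted as tolerating food at 72 and 96 h drop out of the count at the end of study, although 8.6.3 records no loss of tolerance.

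**Working it through.** The plan states no figure for the end-of-study proportion, so there is none to reproduce. The check applies both rules to the same hypothetical patients.

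**Rules used**
- Primary status (SAP 8.6.3): event at the first tolerated solid meal with no later failed in-hospital meal, procedures excepted. An inpatient is censored only if not discharged and not tolerating.
- 48, 72 and 96 h (SAP 8.7.1): *yes* if the 8.6.3 time has been reached by that hour.
- End of study as written (SAP 8.7.1): *no* if not discharged.
- End of study from 8.6.3: *yes* if the 8.6.3 time falls at or before the end of study.

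| Hypothetical patient | Primary | 48 / 72 / 96 h | End of study, as written | End of study, from 8.6.3 |
|---|---|---|---|---|
| Sustained tolerance from 60 h, inpatient at Day 30 | event at 60 h | no / yes / yes | **no** | **yes** |
| Sustained tolerance from 240 h, inpatient at Day 30 | event at 240 h | no / no / no | **no** | **yes** |
| Never tolerated, inpatient at Day 30 | censored | no / no / no | no | no |
| Sustained tolerance from 60 h, discharged at 96 h | event at 60 h | no / yes / yes | yes* | yes |

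*Inferred from the opening sentence of 8.7.1. No explicit end-of-study rule is written for discharged patients.

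The rules disagree only in the first two rows: sustained tolerance under 8.6.3 and no discharge.

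**Can such a patient arise?** Yes. Protocol 5.3 lists food tolerance as one of three criteria for medically indicated discharge. The other two are pain control and infection: "There is no clinical evidence of an infection necessitating continued hospitalization". A patient can meet the first and remain in hospital because of either of the others.

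**Is the rule needed because data are missing?** No. Protocol 8.10 has sites determine, for patients still in hospital on Day 30, whether and when solid food was tolerated in the preceding 48 hours. SAP 8.7.1 also has a separate sentence that imputes *no* when status is unknown.

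**Size**
- Patients per arm: 54 (SAP Section 4).
- Shift per affected patient: 1/54 = 0.0185, or 1.9 percentage points.
- For an assumed 1 to 3 affected patients in an arm: 1/54 = 1.9 points to 3/54 = 5.6 points. The 1 to 3 is an illustration and does not come from the documents.

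**The case against.** There are five points on the other side.

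- **The affected group is narrow.** Because 8.6.3 requires tolerance to be sustained, a patient who tolerates food at 60 h and fails a meal on Day 20, without a qualifying procedure, is not an event at 60 h. It would be too strong to say that any earlier tolerated meal is overridden. This stands and limits the point.

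- **The time point is minor.** The endpoint lists in Protocol 2.3 and SAP 5.1 name 48, 72 and 96 h and discharge, but not the end of study. A reader might infer from the conflict with 8.6.3 that the primary result is at risk. It is not: the sentence changes neither the primary analysis nor the 48, 72 and 96 h rates. The end-of-study proportion is nevertheless tested.

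- **Phase 2a does not show that such patients occur.** A reader might point to the 30.0-day maximum stay on supportive care alone (Protocol 1.5.2). The same section gives a maximum time to tolerance of 720 h in that group, and 720/24 = 30.0 days. On Auxora the maxima also match: 440/24 = 18.3 days to tolerance and an 18.3-day stay. There are no patient-level data, but the longest stays may belong to patients who did not tolerate food until the end, if at all. A patient with no tolerance by Day 30 is *no* under both rules.

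- **The sentence may be meant for the discharge time point.** It follows the discharge rule, which compares tolerance time with discharge time and does not clearly cover patients who have no discharge time. That reading is plausible, but the text names the end of study, which is analysed separately, so it still needs correcting. The objection also shows that the sentence should not simply be deleted.

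- **Continued hospitalisation or death may be intended as failure.** The SAP does not say so. Section 8.7.3 names a composite strategy where it uses one. Section 8.7.1 names only a treatment-policy strategy, for prohibited medication and treatment discontinuation. Death is listed as an intercurrent event in 8.6.2, but 8.7.1 assigns it no strategy.

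**Conclusion.** The point holds, within limits. Followed literally, 8.7.1 misclassifies patients with sustained tolerance who are never discharged, against the definition it says it uses. Only the end-of-study proportion, its confidence interval and its CMH comparisons are affected.

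The size is unknown because the documents give no count of such patients. It is 1.9 points per patient with 54 in the arm. The denominator may be slightly smaller, since the analysis set requires at least some study drug.

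A reader might infer that the rule favours Auxora, because a shorter stay would leave more placebo patients forced to *no*. The documents do not establish this. A shorter typical stay is not enough: the arms would have to differ in the number of food-tolerating inpatients at Day 30, and nothing shows that they will. The mixing of tolerance with length of stay does not depend on that condition.

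The conclusion assumes that the end of study in 8.7.1 means the patient's own Day 30 visit. Protocol 3.2 defines the term for the whole trial, by the last patient's visit.

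**What to change.** In SAP 8.7.1:

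1. Replace the end-of-study sentence with a rule based on the 8.6.3 event: *yes* if the 8.6.3 time to tolerance is at or before the end of study, whether or not the patient was discharged; otherwise *no*. This also supplies the missing rule for discharged patients.
2. Keep a separate, explicit sentence for the status at discharge of patients who were never discharged.
3. State how a patient who tolerated food and then died in hospital is scored. Without this, item 1 would make that patient *yes* by default.
4. If continued hospitalisation is meant to count as failure, say so as a composite strategy, as 8.7.3 does for its own endpoint, and label the proportion accordingly.

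The cost is a few sentences in the SAP before unblinding. No new data are needed, and no stated sample size or power changes.

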8.7.2 Time to Medically Indicated Discharge

The time to medically indicated discharge is the number of days from the SFISD to the first date of meeting the criteria defining medically indicated discharge:

- the patient tolerates solid food, as defined by the main analytical approach; and
- abdominal pain is controlled or resolved, which will be defined by a reduction in pain, as assessed by the PNRS scale, of ≥50% from the peak level in the first 24 hours and no use of opioids; and
- there is no clinical evidence of an infection requiring continued hospitalization.

In patients who do not meet the criteria for medically indicated discharge when discharged from the hospital, the time to medically indicated discharge will be defined as 8am on the first of three consecutive days where the 4 criteria are met for the mGCSI-DD as defined in 8.6.3. If a patient is discharged not meeting the criteria for medically indicated discharged and does not meet criteria for the mGCSI-DD or has not completed the mGCSI-DD, the time to medically indicated discharge will be censored at 168 hours. If the patient dies while hospitalized, the time to medically indicated discharge will be censored at Day 30.

The time to medically indicated discharge will be summarized using Kaplan-Meier analyses. The medians and quartiles of time-to-events will be summarized for each study group. The time to medically indicated discharge will be compared between each Auxora treatment group and placebo group using stratified log-rank test stratified by sex (male or female) and the risk for organ failure (higher or lower). Prohibited immunosuppressive medications or immunotherapies and treatment discontinuation will be ignored (treatment policy strategy).

Protocol CM4620-203 CONFIDENTIAL Page 19 of 31

The proportion and 95% CI of patients who meet the medical discharge criteria by the 96-hour visit and the date of discharge will be displayed using a Clopper-Pearson interval and will be compared between each Auxora treatment group and placebo group using a Cochran-Mantel-Haenszel test stratified by the eCRF recorded sex (male or female) and the risk for organ failure (higher or lower) based on eCRF data. Prohibited immunosuppressive medications or immunotherapies and treatment discontinuation will be ignored (treatment policy strategy).

The correlation between meeting the medically indicated discharge criteria on the day of discharge with each of the following events, hospital readmission for acute pancreatitis, the development of pancreatic necrosis/necrotizing pancreatitis, and worsening CTSI score at Day 30 from Screening, will be summarized by treatment groups by Matthews correlation coefficient (MCC).

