8.2 Baseline Assessment

Perform the following prior to randomization:

- Record height and weight
- Record SpO₂ and the FiO₂ (see Section 8.12.6) closest but prior to the time of randomization
- Record the patient's pain using the pain numeric rating scale (PNRS) scale closest but prior to the time of randomization
- Record the patient's symptoms using the mGCSI-DD worksheet closest but prior to the time of randomization
- Draw blood samples for Serum Procalcitonin and Serum Chemistries analyze at local lab.
 - o If already performed at local lab as SOC, record results. Testing may be performed on blood drawn in the previous 12 hours of randomization.
- Draw blood sample for Serum IL-6 send to central lab. May be performed on blood drawn in the previous 12 hours of randomization
- Obtain urine sample for Urine NGAL send to central lab. May be performed on urine collected in the previous 12 hours of randomization

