8.3 Randomization Using IXRS System

8.4 Start of First Infusion of Study Drug (SFISD)

The SFISD should begin within 8 hours of the patient or LAR providing informed consent.

Perform the following procedures immediately prior to the SFISD:

- Record concomitant medications
- Infuse the first dose of study drug
 - Record the time of the SFISD
 - o Record the time when the infusion is finished
 - Draw blood sample for PK as soon as possible after completion of the first infusion of study drug (within +2 hours)
- Begin Enhanced Recovery Strategy for Tolerance of Solid Food (see Section 5.2) and continue daily until patient discharge.

8.5 24 hours

24 hours from the SFISD:

- Record concomitant medications
- Record vital signs closest to the scheduled time of assessment
- Record the patient's pain using the PNRS closest to the scheduled time of assessment
- Record SpO₂ and the FiO₂ (see Section 8.12.6) closest to the scheduled time of assessment
- Determine if, and when the patient tolerated solid food in the previous 24 hours (see Section 5.2)
- Determine if the patient met the medically indicated discharge criteria in the previous 24 hours (see Section 5.3)
- Perform AE/SAE assessment
- Prior to the infusion of the second dose of study drug:
 - Draw blood samples for CBC, differential, platelets, Serum Procalcitonin and Serum Chemistries - analyze at local lab. Testing may be performed on blood drawn in the previous 12 hours.
 - Draw blood sample for Serum IL-6 send to central lab. Testing may be performed on blood drawn in the previous 12 hours.
 - O Draw blood sample for PK prior to the infusion of the second dose of study drug (within -30 min) send to central lab.
 - Obtain urine sample for Urine NGAL-send to central lab. Testing may be performed on urine collected in the previous 12 hours.
- Start the infusion of second dose of study drug 24 hours (±1 hour) from the SFISD (see Section 5.3)
 - o Record the time when the infusion starts and finishes

8.6 48 hours

48 hours from the SFISD:

- Record concomitant medications
- Record vital signs closest to the scheduled time of assessment
- Record the patient's pain using the PNRS closest to the scheduled time of assessment
- Record SpO₂ and the FiO₂ (see Section 8.12.6) closest to the scheduled time of assessment
- Determine if, and when the patient tolerated solid food in the previous 24 hours (see Section 5.2)

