Appendix 4. Pain Numeric Rating Scale (PNRS)

Pain Numeric Rating Scale

1. On a scale of 0 to 10, with 0 being no pain at all and 10 being the worst pain imaginable, how would you rate your pain RIGHT NOW.

0 1 2 3 4 5 6 7 8 9 10

No Worst Pain
Pain Imaginable

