8.1.4 Derived Variables

8.1.4.1 Definition(s) of Baseline(s)

Unless otherwise specified, the baseline values are the last available assessment before or at the time of the SFISD. If multiple measurements are recorded on the same day, the last measurement recorded prior to or at the time of the SFISD will be used as the baseline value. If these multiple measurements occur at the same time or time is not available, then the average of these measurements (for continuous data) or the worst among these measurements (for categorical data) will be considered as the baseline value.

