8.1.4.2 Study Time

For patients enrolled in the study, the first dose of study medication will be administered at study hour 0. The study time in hours for an event is defined as event date and time – date and time of SFISD. The study day is defined as event date – date of SFISD + 1 day.

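### SAP 8.7.2 leaves the reference for the 50% pain reduction undefined; read on the study clock it is a single post-dose score, which makes the test stricter for patients whose pain falls early

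*SAP*

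**What the plan says.** SAP 8.7.2 counts this endpoint from the start of the first infusion of study drug (SFISD): "The time to medically indicated discharge is the number of days from the SFISD to the first date of meeting the criteria". There are three criteria: solid food tolerance, pain controlled or resolved, and no infection that requires further hospital stay. The pain criterion is a reduction, "as assessed by the PNRS scale, of ≥50% from the peak level in the first 24 hours and no use of opioids".

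The other relevant text is as follows.

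- SAP 8.1.4.2, on study time: "the first dose of study medication will be administered at study hour 0".
- SAP 8.1.4.1, on baseline: "the baseline values are the last available assessment before or at the time of the SFISD". Section 8.7.2 does not use the word baseline for the pain reference.
- Protocol 8.2, before randomization: "Record the patient's pain using the pain numeric rating scale (PNRS) scale closest but prior to the time of randomization".
- Protocol 8.5, at the 24 h visit: "Record the patient's pain using the PNRS closest to the scheduled time of assessment". The same instruction recurs at 48 h, 72 h and later visits. The schedules in both documents show no pain numeric rating scale (PNRS) score at the SFISD visit.
- Protocol Appendix 4 gives the question put to the patient: "how would you rate your pain RIGHT NOW".

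SAP 8.7.2 compares each Auxora group with placebo by stratified log-rank test. It also compares the proportions meeting the criteria by the 96-hour visit and by the date of discharge, and correlates meeting them on the day of discharge with later events.

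**The concern.** A reference for percentage improvement should not itself be changed by treatment. If the 24 hours run from hour 0, as the endpoint does, the pre-randomization score lies outside the window and the peak is one post-dose score. A patient who improves quickly then has to reach a lower absolute score than one who improves slowly.

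At stake is the between-group comparison on a secondary endpoint. A drug that relieves pain in the first day would lose part of its advantage on the pain component. Patients discharged without meeting the criteria would pass to the diary rule or to censoring at 168 h. Two programmers could also read the sentence differently and obtain different event times from the same data.

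**Working it through.** **Plan's own figure.** Neither document gives a pain score, pain-control rate or power figure for this criterion, so there is nothing to reproduce.

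**Step 1: readings in the window.** Scheduled PNRS readings are Baseline (before randomization), 24 h, 48 h, 72 h and later. From hour 0 to the 24 h visit there is one; with Baseline counted there are two. Because the question asks about pain at that moment, the 24 h score is not a worst-in-24-hours value.

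**Step 2: the threshold.** Let R be the reference and Y the current score. The rule is (R − Y)/R ≥ 0.5, that is, Y ≤ 0.5 × R for R > 0.

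| Scores (Baseline, 24 h, 48 h, 72 h) | R = 24 h score | R = higher of Baseline and 24 h |
|---|---|---|
| Patient A: 8, 3, 2, 2 | threshold 1.5; not met at 48 or 72 h | threshold 4; met at 24 h (3 ≤ 4) |
| Patient B: 8, 8, 4 | threshold 4; met at 48 h | threshold 4; met at 48 h |

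Under the 24 h reference, A has less pain than B at 24 h and at 48 h, yet is not scored as controlled when B is. Two further consequences follow. At 24 h, Y = R and the reduction is 0%, so the earliest possible control is 48 h in every arm. If R = 0, the fraction is undefined.

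**Step 3: size on the pain component, under assumed paths.** Assumptions: Baseline mean 7.5 (SD 1.5), reading noise SD 0.8, and integer scores read daily to 240 h. Patients not controlled by then count as 264 h. Pain declines exponentially (half-life 60 h) or linearly (0.05 points per hour) towards a floor of 0, 1 or 2. There are 200,000 simulated patients per arm. The drug lowers pain by 40% from the first post-dose reading, with the same decline rate afterwards. Entries are mean hours to pain control, placebo/drug, with the drug's advantage in brackets.

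| Path, floor | R = 24 h score | R = higher of Baseline and 24 h |
|---|---|---|
| Exponential, 0 | 87/82 (5) | 65/30 (35) |
| Exponential, 1 | 102/101 (1) | 76/33 (43) |
| Exponential, 2 | 124/137 (−13) | 94/39 (55) |
| Linear, 0 | 92/65 (27) | 80/29 (51) |
| Linear, 1 | 93/70 (23) | 80/29 (51) |
| Linear, 2 | 96/100 (−4) | 80/30 (50) |

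With the 24 h reference the mean R is 5.7 to 6.3 on placebo and 3.3 to 3.9 on drug. With the higher-of-two reference it is 7.5 in both arms.

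If the drug instead speeds the decline 1.5-fold throughout, the advantage in the same six settings is 15, 18, 20, 21, 22 and 18 h with the 24 h reference. With the higher-of-two reference it is 16, 19, 24, 22, 22 and 21 h. The loss is 0 to 4 h.

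**Step 4: adding food tolerance.** A second assumed model has Baseline mean 7 (SD 1.8) and noise SD 1.3. Pain at 24 h is 50% of Baseline on drug and 80% on placebo, then falls by a fixed percentage per day. Food tolerance is exponential, independent of pain, with the design medians of 72 and 144 h (SAP section 4). Opioid use and infection are not modelled. Entries are drug-minus-placebo differences in the proportion meeting both criteria.

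| Daily fall after 24 h | Time | R = 24 h score | R = higher of two |
|---|---|---|---|
| 10% | 96 h | 21 points | 34 points |
| 20% | 72 h | 15 points | 27 points |
| 20% | 96 h | 20 points | 26 points |
| 25% | 96 h | 20 points | 25 points |
| 40% | 96 h | 21 points | 23 points |

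At 96 h, the time point the SAP uses, the loss runs from 13 points (34 − 21) to 2 points (23 − 21). The drug arm stays ahead in every row.

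**The case against.** The strongest reply is that nothing in the SAP excludes the Baseline score. Section 8.7.2 does not tie the 24 hours to post-dose readings, and section 8.1.4.2 defines study time for events, not this window. The word peak suggests more than one reading, and the two scheduled candidates are Baseline and 24 h. On that reading the rule already equals the fix. This stands as a possible intention, but it is not what the text states. The endpoint's clock starts at SFISD, and the SAP has a defined term for baseline that it does not use here.

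A reader might infer more than the documents support:

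- *That an early-relief arm is scored as controlled later than placebo.* This happened in 2 of the 6 early-drop settings and in none of the 6 with a steadily faster decline. The usual result is a reduced or lost advantage.
- *That a visit at 24 to 25 h leaves no reading at all.* SAP 8.1.6 bases the analysis on eCRF visits, so a nominal 24 h score counts.
- *That a patient with a low 24 h score can never have an event.* After discharge the diary rule in 8.7.2 can still supply one.
- *That this is the main supporting secondary endpoint.* SAP 5.1 lists it among the secondary endpoints without ranking. The primary objective that uses it compares food-tolerance responders with non-responders, so the between-arm argument does not carry over directly.

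It is also fair to say that pain delays the endpoint only when it is the last criterion met. For any one patient the delay in the endpoint is no larger than the delay in the pain part.

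**Conclusion.** The point holds as an undefined reference whose natural reading on the study clock is post-treatment. That there is one scheduled post-dose score in the window, no possible control before 48 h, and no rule for a 24 h score of 0 follows from the documents on that reading and needs no assumption.

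The direction is also clear: early relief lowers the reference and makes the 50% test stricter for those patients. The size is not known, because the documents contain no pain data and the result depends on the shape of the pain path. In the assumed settings the loss of advantage on pain alone ranges from almost nothing (steadily faster decline) to complete loss with reversal (early drop, then residual pain at a floor of 2). Because food tolerance, no opioid use and no infection are also required, the shortfall that this rule causes within an arm is smaller on the endpoint than on pain alone. If Baseline is counted, the arm-dependence largely disappears. The point merits a change to the SAP because the two readings give materially different results.

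**What to change.** In SAP 8.7.2, define the reference as the higher of the pre-dose Baseline PNRS and the 24 h visit PNRS, the latter identified by eCRF visit label. Treat the PNRS part as met when the current PNRS is at most 50% of that reference. A current score of 0 then always meets it. A reference of 0 should not by itself count as control: with both readings 0 and a later score of 6, the threshold is 0 and the part is not met. The no-opioid condition is unchanged.

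The cost is one or two sentences, settled before unblinding. Both scores are already scheduled, and the Baseline score is recent when the schedule is kept: "The SFISD should begin within 8 hours of the patient or LAR providing informed consent". One small dependence remains, in patients whose pain is higher at 24 h than at Baseline. With Baseline 8 and a 24 h score of 9, the threshold is 4.5 instead of 4. Using Baseline alone would remove it, but would give up the idea of a peak.
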